**A multi-center, double-blind, randomized, parallel design study to compare the effectiveness of suvorexant versus placebo on sleep pressure and circadian rhythm in hypertensives with insomnia:
The Super 1 study**

[figure not shown]
(To compare the effectiveness of suvorexant vs placebo on sleep pressure in hypertensives with insomnia: Super 1)

Study Protocol and Statistical Analysis Plan

2016/6/10 ver.1.2

Principal investigator : [name]
Division of Cardiovascular Medicine,
Jichi Medical University School of Medicine
Study duration : 2016/6/16~2018/9/30

Study Title:	A multi-center, double-blind, randomized, parallel design study to compare the effectiveness of suvorexant versus placebo on sleep pressure and circadian rhythm in hypertensives with insomnia: The Super 1 study
Objectives:	The purpose of this study is to compare the effectiveness and safety of suvorexant versus placebo on sleep blood pressure and circadian rhythm in hypertensives with insomnia.
Study Subjects:	Patients with hypertension and insomnia
Inclusion criteria:	
(1) At pre-enrollment
 
Patients who meet the following criteria are eligible for the study:
 
 1. Patients who give written consent of agreement to voluntarily participation in the clinical study 2. Age 20 years or older 3. Sex: Male or female 4. Treatment classification: Outpatient 5. Hypertensive patients who meet at least one of the following: 
 - Clinic systolic blood pressure (SBP) <160 mmHg - Under antihypertensive medications 6. Patients with insomnia who meet at least one of the following: 
 - Patients with any one of the following symptoms twice a week and at least 1 month-continuation: difficulty initiating sleep (time to sleep onset \geq2 hours longer than usual), difficulty maintaining sleep (awakening \geqtwice in the night), difficulty sleeping deeply (no soundly asleep feeling at the time of awakening in the morning), early morning awakening (awakening \geq2 hours earlier in the morning than usual) - Patients with interference with social or occupational function due to the above insomnia symptoms 
(2) At enrollment
 
Patients who meet the following criteria at the end of run-in period are eligible for the study:
 
 1. Stable unchanged antihypertensive medication for run-in period 2. Average morning home SBP \geq135 mmHg during 5 days before the end of run-in period
Exclusion criteria:	
Patients who meet any of the following criteria are not eligible for the study:
 
 - Patients with serious liver and respiratory disease - Patients with secondary hypertension - Patients with sleep apnea syndrome - Patients with history of narcolepsy or cataplexy - Patients with history of organic cerebral disorders - Patients with history of hypersensitivity to suvorexant - Patients received CYP3A strongly-inhibitors including itraconazole, clarithromycin, ritonavir, saquinavir, nelfinavir, indinavir, telaprevir and voriconazole at the start of the run-in period - Patients received suvorexant and other hypnotic at the start of the run-in period - Patients with average clinic SBP of \geq160 mmHg at the start of the run-in period - Patients who are breast-feeding, pregnant, possibly pregnant, or plan to become pregnant

	
 - Patients who are considered not to be eligible for this study by their investigator or sub-investigator
Study drug:	
(1) Dosage Form : Film coat tablet Suvorexant 15mg tablet/20mg tablet, Placebo 15mg tablet/20 mg tablet
 
(2) Package : Suvorexant 15mg tablet: 21 tablets in a plastic bottle Suvorexant 20mg tablet: 21 tablets in a plastic bottle Placebo 15mg tablet: 21 tablets in a plastic bottle Placebo 20mg tablet: 21 tablets in a plastic bottle
 
(3) Storage : Investigational products are to be stored at room temperature. Store in the bottle just before taking to protect from light and moisture.

Study design:	
This study is a multi-center, double blind, randomized, parallel design.
  
The diagram illustrates the study design timeline. It starts with a 'Run-in period' leading to 'Visit 1'. Following 'Visit 1' is a '5 days before Visit 2' period. 'Visit 2 (Week 0)' is marked with a downward arrow indicating 'Randomization if morning SBP ≥ 135mmHg by HbPM'. This leads to the 'Treatment period' with 'Visit 3' and 'Visit 4 (Week 2)'. A blue arrow at the top indicates 'Unchanged antihypertensive medication throughout the study periods'. Red arrows at the bottom indicate 'Home blood pressure monitoring (morning and evening)' and 'ABPM' (Ambulatory Blood Pressure Monitoring) at Visit 1 and Visit 4.

Outcomes	
Primary Outcome :
 
 - Change in sleep systolic blood pressure (BP) at week 2 from week 0 by ambulatory blood pressure monitoring (ABPM) 
Secondary Outcomes :
 
 - Percent of patients changed from the non-dipper to the dipper during the treatment period - Change in morning SBP at week 2 from week 0 by ABPM and home blood pressure monitoring (HbPM) - Change in standard deviation (SD) and coefficient of variation (CV) of sleep SBP at week 2 from week 0 by ABPM - Change in the total sleep time - Change in the time to sleep onset - Correlation of changes in nighttime BP parameters with changes in sleep quality parameters - Correlation of changes in urinary albumin-to creatinine ratio (UACR)/NT-proBNP
Study size:	80 patients in total

Statistical Analysis:	
Study size calculation:
 
At 80% power and assuming adjusted mean differences in the change from baseline in mean nighttime SBP with suvorexant vs placebo of -5.0 mm Hg with a standard deviation (SD) of 7.5 mm Hg in both groups, it was calculated that 36 patients in each group would be required (72 in total). The target enrollment was set at 80 patients to allow for a 10% withdrawal rate.
 
Statistical analysis methods:
 
All analyses will be conducted in the full analysis set (FAS), which included all enrolled participants who received their assigned therapy at least once after randomization and who had made 24 - hour ABPM recordings at least once. The safety analysis set (SAS) included all randomized participants who had received the assigned therapy at least once during the study period. Efficacy analyses for BP values will be conducted in the FAS, and safety will be determined in the SAS.
 
Intergroup comparisons will be tested with a t-test for continuous variables, and Pearson's chi-squared test or Fisher's exact test will be used for dichotomous data. Mixed - effects model repeated measures (MMRM) analysis will be used to compare the changes in SBP. MMRM included the randomized study group, the time points (baseline, week 2), the interaction between the study group and time points as fixed effects, and age and sex as covariates. P - values for interactions between baseline SBP and the change from baseline in SBP will be determined using the general linear model, adjusted for age and sex. All statistical analyses will be performed with SAS version 9.4 software (SAS Institute Inc, Cary, NC, USA). P - value is two - tailed, and its <0.05 is considered statistically significant.

-----------------------	--

Schedule of examination, observation and assessment

	Run-in period ^{※1}	Treatment period			Termination
	Visit 1	Visit 2	Visit 3	Visit 4	
	- 4 week	Week 0	Week 1	Week 2	
Informed consent	○				
Pre-enrollment ^{※2}	○				
Enrollment ^{※2}		○			
Randomization		○			
Administration of study drug ^{※3}			←————→		
Study drug adherence				○	○
Concomitant medications	○	○	○	○	○
Demographic characteristics	○				
Subjective symptoms, Objective findings	○	○	○	○	○
Height, Weight, Abdominal circumference ^{※4}	○	○		○	○
Home blood pressure monitoring (morning, evening) ^{※5}		←————→			
Clinic blood pressure monitoring	○	○	○	○	○
Ambulatory blood pressure monitoring (ABPM) ^{※6}		○		○	○ ^{※9}
Blood test : NT-proBNP		○		○	○
Urinalysis: Albumin		○		○	○
Urinalysis: Creatinine		○		○	○
Adverse events ^{※7}	←————→				
Sleep diary ^{※8}	←————→				

※1 At least 3 weeks for the run-in period

※2 Pre-enrollment and enrollment will be registered on web system.

※3 Patients will orally receive study drug once daily before bedtime during the treatment period (from the next day of week 0 to the day of Week 2).

※4 Height will be measured at the start of run-in period (Visit 1).

※5 Home blood pressure monitoring (morning, evening) should be performed every day from 5 days before week 0 to the next day of week 2.

※6 ABPM will be performed at the start of treatment (Week 0) and the end of treatment (Week 2) for 26 hours until the following day.

※7 Adverse events will be collected from the start of run-in period (Visit 1) to completion of this study (the next day of visit 4).

※8 Patients will be asked to record "Sleep diary" from the start of run-in period (Visit 1) to completion of this study (the next day of visit 4).

※9 ABPM will be performed as much as possible at the termination.

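### Does the plan need changing because its two correlation outcomes have no stated method and no stated handling of treatment arm?

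*Combined protocol and SAP*

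**What the plan says.** The Outcomes section lists seven secondary outcomes. Two are correlations: "Correlation of changes in nighttime BP parameters with changes in sleep quality parameters" and "Correlation of changes in urinary albumin-to creatinine ratio (UACR)/NT-proBNP". The same list includes "Change in the total sleep time - Change in the time to sleep onset" and "Change in standard deviation (SD) and coefficient of variation (CV) of sleep SBP", so the sleep and nighttime BP measures also appear as outcomes in their own right.

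The statistical methods name a t-test for comparisons between groups, chi-squared or Fisher tests for dichotomous data, an MMRM for changes in SBP, and a model relating baseline SBP to SBP change, which "will be determined using the general linear model, adjusted for age and sex". None is a correlation analysis. On population the section says "All analyses will be conducted in the full analysis set (FAS", and the FAS contains both arms. The sample size rests on an SBP reduction of "5.0 mm Hg with a standard deviation (SD) of 7.5 mm Hg in both groups".

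**The concern.** Three things are unstated for the BP-sleep correlation: the coefficient, the variables on each side, and whether the arms are pooled, separated or adjusted for. The biomarker item could mean one marker against the other, or each marker against a variable it does not name.

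Arm handling matters most. The trial is sized for a drug effect on nighttime SBP, and sleep time and sleep onset are outcomes of the same drug. If treatment moves both SBP and sleep, patients on active drug cluster at one corner of the scatter plot and patients on placebo at the other. A correlation over all patients is then non-zero even if, within each arm, a patient's sleep change says nothing about that patient's SBP change. This is the only listed outcome that ties sleep change to BP change, so a reader could take the result as evidence that better sleep lowers pressure when it only restates two arm differences.

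**Working it through.** **The plan's own figure.** Inputs from the study size calculation: difference 5.0 mm Hg, SD 7.5 mm Hg, power 80%, two-sided 0.05. n per group = 2 × (1.960 + 0.842)² × (7.5/5.0)² = 2 × 7.85 × 2.25 = 35.3, so 36 per group and 72 in total; 72/0.9 = 80. The stated 36, 72 and 80 reproduce. A t-based calculation gives 36.3 per group and 79.7% power at 36, close enough.

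**Pooled correlation.** Let d1 be the standardised SBP effect, 5.0/7.5 = 0.667. Let d2 be the standardised sleep effect (not in the documents, so a range is assumed) and rw the within-arm correlation. For two equal arms and total sleep time, where improvement is an increase:

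pooled r = (rw − d1·d2/4) / √[(1 + d1²/4)(1 + d2²/4)]

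With rw = 0 and d1²/4 = 0.111:

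- d2 = 0.2: −0.0333/√(1.111 × 1.010) = −0.0333/1.059 = −0.03
- d2 = 0.5: −0.0833/√(1.111 × 1.0625) = −0.0833/1.087 = −0.08
- d2 = 0.8: −0.1333/√(1.111 × 1.160) = −0.1333/1.135 = −0.12

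For time to sleep onset, improvement is a decrease, so the artefact has the same size and a positive sign.

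**Rejection rates.** Normal changes, 36 per arm, rw = 0, 40,000 simulated trials per row. The simulation error is √(0.05 × 0.95/40,000), about 0.1 point, for rates near 5%.

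| Sleep effect (SD, assumed) | Pooled, p<0.05 | Adjusted for arm, p<0.05 |
|---|---|---|
| 0 | 4.8% | 4.9% |
| 0.2 | 5.9% | 5.0% |
| 0.5 | 9.7% | 4.9% |
| 0.8 | 16.8% | 5.1% |
| 1.0 | 22.4% | 5.1% |

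With all 80 patients the pooled rates from 0.2 to 1.0 SD are 5.8, 10.3, 18.3 and 24.0%. A pooled rank correlation behaves like the Pearson one (6.0, 9.7 and 16.5% at 0.2, 0.5 and 0.8 SD).

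**When a link exists.** At rw = −0.30 the pooled r averages −0.31, −0.35 and −0.38 for sleep effects of 0.2, 0.5 and 0.8 SD; adjusted for arm it averages −0.30. With no sleep effect the pooled value is slightly diluted: −0.30/√1.111 = −0.285. Power at rw = −0.30 with 72 patients is about 73% adjusted.

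**Does the plan call for the pooled version?** The population sentence defines a set of patients. A pooled correlation, separate correlations by arm and a partial correlation adjusted for arm are all computed in the FAS. Nothing in the methods selects the first.

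**Are the data there?** The schedule has ABPM, NT-proBNP, urinary albumin and urinary creatinine at Weeks 0 and 2, and a sleep diary from Visit 1 to the end. An arm-adjusted analysis costs one degree of freedom. Either reading of the biomarker item can be computed from what is collected.

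**The case for a change.** The strongest case for a change is that this document is both protocol and SAP and points to no other analysis document, so its silence leaves two competent statisticians free to produce different analyses. With an unadjusted 0.05 threshold and undefined parameters, there is also room to choose. The listed measures alone give 3 × 2 = 6 pairs (mean, SD and CV of sleep SBP against total sleep time and time to sleep onset). If all six tests were independent, the chance of at least one false positive would be 1 − 0.95⁶ = 26.5%. Writing down one lead pair and an arm term would be cheap.

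Part of this stands. The methods are missing, the biomarker item is unclear, and the pooling arithmetic is right. But the six pairs are an inference from other bullets, the 26.5% is an upper illustration because the measures overlap, and an unadjusted 0.05 applies to every secondary outcome here. The misreading is also not one the plan makes. The stated objective is to "compare the effectiveness and safety of suvorexant versus placebo on sleep blood pressure and circadian rhythm", with no claim that sleep mediates the BP effect. A pooled correlation is a legitimate description, and it misleads only if read as a within-arm link.

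**Conclusion.** The concern does not call for a change. What the text shows is silence about two supportive outcomes, not a wrong analysis. The distortion needs two things the plan does not state: that the arms are pooled without an arm term, and that the drug has a sizeable effect on sleep. Given pooling, the excess false-positive rate is under 1 point at a sleep effect of 0.2 SD, about 5 points at 0.5 SD (9.7 against 4.9%) and about 12 points at 0.8 SD (16.8 against 5.1%). These figures assume normal changes, equal arms and the planned SBP effect.

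An analyst who adjusts for arm or reports by arm stays within the plan and removes the problem. The analyst can also settle which markers and parameters are paired, and the report should say what was done. The unclear UACR/NT-proBNP wording is a drafting gap of the same kind. The primary outcome, the sample size and the comparisons of suvorexant with placebo do not depend on any of this.

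### Does the UACR/NT-proBNP correlation outcome need a named partner, a coefficient and a log scale before the plan can stand?

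*Combined protocol and SAP*

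**What the plan says.** The synopsis ends its secondary outcomes with two correlation items. The first names both sides: "Correlation of changes in nighttime BP parameters with changes in sleep quality parameters". The second does not: "Correlation of changes in urinary albumin-to creatinine ratio (UACR)/NT-proBNP".

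The paragraph on statistical analysis methods names no correlation coefficient. It sets a general rule for comparing the arms, "Intergroup comparisons will be tested with a t-test for continuous variables", and limits its two models to blood pressure: "Mixed - effects model repeated measures (MMRM) analysis will be used to compare the changes in SBP" and "P - values for interactions between baseline SBP and the change from baseline in SBP will be determined using the general linear model". No transformation, rank method or baseline covariate is given for the biomarkers.

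The schedule of examinations lists "Blood test : NT-proBNP", "Urinalysis: Albumin" and urinary creatinine at Week 0, at Week 2 and at termination. A paired baseline and follow-up value is therefore planned for each biomarker.

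**The concern.** A correlation needs two variables and this item supplies only one side. At least three readings are open: UACR change with NT-proBNP change, each biomarker with nighttime blood pressure, or each biomarker with sleep quality. The coefficient, the scale of change and the handling of the two arms are also left open.

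There is also a plausible efficiency argument. If the biomarkers are right-skewed, a few patients with high values dominate the absolute changes. In simulated log-normal data with between-patient log-SD 0.8 to 1.3, the two most extreme of 72 patients carry 42–62% (median) of the sum of squares of absolute change, against 17% on the log scale. A Pearson coefficient or a t-test on absolute change could then miss a real signal. At stake would be the power and the readability of one secondary outcome.

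**Working it through.** **1. The plan's own figure.** The sample size rests on nighttime SBP alone: difference 5.0 mm Hg, SD 7.5 mm Hg, two-sided 5%, 80% power.

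n per arm = 2 × (1.960 + 0.842)² × 7.5² / 5.0² = 35.3, rounded up to 36. That gives 72 in total, and 72 / 0.90 = 80. The stated figures reproduce. No power is claimed for UACR or NT-proBNP.

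**2. What a correlation can detect at this size.** By Fisher's z, the smallest |r| with 80% power is tanh(2.802 / √(N − 3)).

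- Arms pooled, N = 72: tanh(2.802 / √69) = 0.33.
- One arm, N = 36: tanh(2.802 / √33) = 0.45.

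For a true r of 0.3 on the correct scale with N = 72, power is Φ(atanh(0.3) × √69 − 1.96) = Φ(0.61) = 73%. This is the benchmark for step 3.

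**3. Does the log scale gain power?** The documents give no distribution, so these inputs are assumptions: log-normal biomarker, between-patient log-SD 0.8 to 1.3 (0.4 as a mild case), within-patient log-SD 0.3 to 0.5, N = 72, true r = 0.3. The biomarker is equally skewed in both rows; only the form of its link to the partner variable differs. Results are simulated power for Pearson's coefficient at log-SD 0.8 to 1.3.

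| Association is linear in | Absolute change | Log change |
|---|---|---|
| log change | 28–49% | 72–75% |
| absolute change | 46–65% | 19–44% |

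Spearman on absolute change gives 56–62% in the first row and 20–45% in the second. In the mild case the gaps are small and again reverse: 61–65% on absolute against 73–74% on log change in the first row, and 70–72% against 60–63% in the second.

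Skewness alone therefore does not decide which scale is better. The form of the association does, and nothing in the documents settles it.

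**4. Comparing the arms on the biomarkers.** With 36 per arm, the same log-SD range and an assumed 30% reduction, a t-test on absolute change has 17–65% power and ANCOVA on the log Week-2 value with log baseline has 57–95%. For an assumed 10% reduction the figures are 5–11% and 10–19%, so neither method is adequate. The null rejection rate is 3–5% for both. The gain at larger effects is real, but none of the listed secondary outcomes is a between-arm difference in UACR or NT-proBNP. The t-test sentence is a general rule and assigns no such analysis.

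**The case for a change.** The strongest contrary case does not depend on skewness at all. The document is titled as both protocol and analysis plan, the item cannot be computed as written, and the item directly above it shows the complete form. Filling the gap would cost only wording, and the choice of partner and coefficient would otherwise be made after the data are seen. All of that is accurate, and a sentence naming the partner, the coefficient, the scale and whether the arms are pooled would make the item easier to read.

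What does not stand is the step from there to a needed change of method. The omission is one of detail and reveals no wrong analysis. The candidate readings are few and all use measurements already scheduled. The claim that a correlation on absolute change is pulled towards zero holds only if the true link is on the log scale. The argument about comparing the arms, although numerically sound under its assumptions, concerns an analysis the plan does not list.

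**Conclusion.** No change to the plan follows. The item is incompletely worded, and an analyst can complete it sensibly by stating the pairing, coefficient, scale and pooling used when reporting. There is no general gain in power from prescribing log change or Spearman: under identical skewness the advantage runs from 28–49% against 72–75% in favour of log change to 46–65% against 19–44% in favour of absolute change, depending on an association that the documents do not describe.

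The preference for baseline-adjusted log-scale ANCOVA would matter only if a between-arm biomarker comparison were added and the values proved right-skewed. All the biomarker power figures rest on assumed log-SDs, an assumed r of 0.3 and assumed reductions of 10% or 30%. The sample size of 36 per arm, the primary outcome and the type I error are untouched on either view.

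### The MMRM for SBP change does not condition on baseline sleep SBP: it is valid, but gives up precision that the scheduled week-0 ABPM would supply

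*Combined protocol and SAP*

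**What the plan says.** The primary outcome, under Outcomes, is "Change in sleep systolic blood pressure (BP) at week 2 from week 0 by ambulatory blood pressure monitoring (ABPM". Under Statistical analysis methods, changes in SBP are compared by a mixed model for repeated measures (MMRM), described as follows: "MMRM included the randomized study group, the time points (baseline, week 2), the interaction between the study group and time points as fixed effects". Age and sex are its only covariates.

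Four other statements bear on the point:

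- The same section gives a general rule: "Intergroup comparisons will be tested with a t-test for continuous variables". That test is unadjusted too.
- Baseline SBP appears in one other model, but only for P-values: "interactions between baseline SBP and the change from baseline in SBP will be determined using the general linear model, adjusted for age and sex". It is not used there for the treatment estimate.
- The full analysis set (FAS) requires treated patients "who had made 24 - hour ABPM recordings at least once", so a patient with only a baseline recording can enter.
- The study size calculation rests on "assuming adjusted mean differences in the change from baseline in mean nighttime SBP", without saying what the adjustment is for.

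Footnote 6 of the schedule sets the measurements: "ABPM will be performed at the start of treatment (Week 0) and the end of treatment (Week 2". By footnote 3, dosing starts the day after week 0, so the week-0 value is a pre-treatment measurement.

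**The concern.** Baseline is in the model, but as an outcome whose group means are free to differ. In a randomised trial those means differ only by chance, and the model makes no use of that fact. Subtracting baseline is the best use of it only when the correlation between the two values is close to 1. At lower correlations the subtraction adds noise.

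Two things follow. The confidence interval is wider than it need be in a trial sized at 80% power with no margin. And a share (1 − rho) of any chance baseline difference passes into the treatment estimate, with opposite sign.

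**Working it through.** **Inputs from the document.** Difference 5.0 mm Hg, SD 7.5 mm Hg in both groups, 80% power, 36 per group (72 in total), 10% withdrawal, 80 enrolled (Study size calculation); two-sided 0.05 (Statistical analysis methods).

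**Inputs assumed.** Neither the correlation rho between baseline and week-2 sleep SBP nor the between-patient SD is given. I take rho = 0.4, 0.6, 0.8 and 0.9, equal variances at both times, and 7.5 as the SD of raw change.

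**1. The plan's own figure.** n per arm = 2 × [7.5 × (1.960 + 0.842) / 5]² = 35.3, rounded up to 36. Then 72 / 0.90 = 80. Both reproduce. With the t distribution (70 df), power at 36 per arm is 79.7%, and 37 per arm are needed to reach 80%.

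**2. What the planned model estimates.** With both values present, group, time and group-by-time saturate the four cell means. Age and sex, read as main effects, are constant within a patient and cancel from the change. The group-by-time term is then (mean change on suvorexant) − (mean change on placebo). Fitted to simulated complete data, the two agreed to rounding error, with SE = 7.5 × √(2/36) = 1.768 mm Hg.

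**3. Variance with and without conditioning.** Let s1 and s2 be the SDs at baseline and week 2.

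- Change: s1² + s2² − 2·rho·s1·s2
- Baseline-adjusted: s2²(1 − rho²)
- Difference: (s1 − rho·s2)², which is never negative

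With s1 = s2 = s, the change variance is 2s²(1 − rho) and the ratio of adjusted to unadjusted variance is (1 + rho)/2.

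**4. Size at 36 per arm.** The adjusted SD is 7.5 × √[(1 + rho)/2 × (1 + 1/67)]. The last factor and the 67 df pay for baseline, age and sex. Power is from the noncentral t. Half-width is t × SD × √(2/36); unadjusted, 1.994 × 1.768 = 3.53.

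| | Unadjusted | rho 0.4 | 0.6 | 0.8 | 0.9 |
|---|---|---|---|---|---|
| Implied between-patient SD (mm Hg) | – | 6.8 | 8.4 | 11.9 | 16.8 |
| Variance ratio | 1 | 0.70 | 0.80 | 0.90 | 0.95 |
| Power at 36 per arm | 79.7% | 91% | 87% | 83% | 81% |
| 95% CI half-width (mm Hg) | 3.53 | 2.97 | 3.18 | 3.37 | 3.46 |
| Per arm for 80% power | 37 | 27 | 30 | 34 | 36 |

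Simulation (40,000 trials per rho, baseline as the only covariate) gave adjusted power of 0.911, 0.870, 0.830 and 0.812.

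**5. Chance imbalance.** About 13% of trials have a baseline difference beyond 1.5 standard errors. In the same simulations:

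| Planned test, type I error | rho 0.4 | 0.6 | 0.8 | 0.9 |
|---|---|---|---|---|
| Those 13% of trials | 15% | 12% | 8% | 7% |
| The other 87% | 3.5% | 4.2% | 4.4% | 4.7% |

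The two rows average to about 5%. ANCOVA stays near 5% in both. A second run of 20,000 trials gave 14%, 11%, 9% and 6% for the first row, so read these to within about a point.

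**6. Baseline-only patients.** With 40 per arm and 4 per arm missing week 2, the identity in step 2 is near-exact. The mean absolute gap was 0.25, 0.20, 0.14 and 0.09 mm Hg (300 trials per rho, REML, unstructured covariance). Mean SEs in mm Hg:

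| | rho 0.4 | 0.6 | 0.8 | 0.9 |
|---|---|---|---|---|
| Planned MMRM | 1.73 | 1.74 | 1.75 | 1.75 |
| ANCOVA | 1.50 | 1.61 | 1.71 | 1.75 |
| Constrained baseline | 1.48 | 1.59 | 1.68 | 1.73 |

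**7. If 7.5 is instead a baseline-adjusted SD.** The SD of change is then 7.5 / √[(1 + rho)/2] = 8.96, 8.39, 7.91 or 7.69, and the planned model has 65%, 70%, 75% or 78% power.

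**The case against.** The strongest reply is that nothing here is an error. The change-score contrast is a legitimate analysis, the sample size reproduces, and the trial meets its stated power without the change. That stands: this is a point about efficiency.

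The gain also cannot be sized from the documents. At rho 0.9 it is about one percentage point of power and one patient per arm, and with 10% withdrawal ANCOVA shows no gain in SE. The larger gains need a low correlation that nothing in the plan supports. This also stands. What survives is the direction: in large samples the adjusted variance is never higher, and at 36 per arm with complete data power did not fall even at rho 0.9 after paying for the covariates.

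The conditional type I errors describe a minority of trials and are offset in the rest, so they show no fault in the overall test. They describe what happens when the arms are visibly unbalanced.

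Three readings of the text are open:

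- Age and sex as main effects is the natural reading, but the plan does not spell it out.
- The MMRM sentence is the more specific and can be taken to govern the primary outcome over the general t-test rule.
- The word *adjusted* may refer to age and sex, and the unadjusted formula does return 36, which fits 7.5 being the SD of raw change. The 65% to 78% power range is therefore a contingency only.

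The main point depends on neither of the last two.

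**Conclusion.** The concern holds. Neither method named for the SBP treatment comparison conditions on baseline sleep SBP, although that value is scheduled before dosing. The planned test is valid, so the loss is one of precision: 30% to 5% of the variance for rho from 0.4 to 0.9, or about 11 to 1 percentage points of power at 36 per arm. These sizes assume equal variances at the two times and 7.5 mm Hg as the SD of raw change. With unequal variances the loss vanishes when the baseline SD equals rho times the week-2 SD. The direction is certain in large samples; the size is unknown and may be small. The change is still worth making because it needs no new data and the plan has no spare power on its own inputs.

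**What to change.** Before unblinding, name one primary analysis of sleep SBP. Either of these serves:

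- **ANCOVA** of the week-2 value (or the change) on treatment, baseline sleep SBP, age and sex. It drops patients who have only a baseline recording.
- **Constrained-baseline longitudinal model**: the planned MMRM without the group main effect, with an unstructured covariance and with age-by-time and sex-by-time terms. It keeps baseline-only patients and so fits the FAS definition better.

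Report the adjusted difference with its 95% CI and make the t-test supportive. State whether 7.5 mm Hg is the SD of raw change or a baseline-adjusted SD.

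The cost is SAP wording, a few lines of code and one degree of freedom for baseline. No new data, visits or patients are needed.

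### Morning home SBP is recorded daily, but its model uses only baseline and week 2, so on-treatment readings from patients without a week-2 value do not inform this secondary outcome

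*Combined protocol and SAP*

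**What the plan says.** - **Outcome.** The secondary outcomes include "Change in morning SBP at week 2 from week 0 by ABPM and home blood pressure monitoring (HbPM").
- **Data.** Note 5 to the schedule of examinations says that home monitoring "should be performed every day from 5 days before week 0 to the next day of week 2". The schedule also has a Week 1 visit (Visit 3), midway through treatment.
- **Model.** Under Statistical analysis methods, an MMRM "analysis will be used to compare the changes in SBP". Its time factor has two levels, "the time points (baseline, week 2"), and its other terms include "the interaction between the study group and time points as fixed effects, and age and sex as covariates". The plan gives no separate model for home SBP, no intermediate home time point and no rule for missing home values.
- **Analysis set.** The full analysis set takes enrolled patients "who received their assigned therapy at least once after randomization and who had made" at least one 24-hour ABPM recording. A week-2 value is not required, so an early stopper with a week-0 ABPM stays in.
- **Early termination.** Note 9 to the schedule reads "ABPM will be performed as much as possible at the termination". It covers ABPM only.
- **Home averaging window.** A 5-day average is defined for eligibility at the end of run-in. No window is given for the week-2 home value.

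**The concern.** Two time points suit ABPM, which is scheduled only at week 0 and week 2. Home SBP has about two weeks of daily on-treatment readings. An MMRM protects against dropout through the outcome data it contains, and the last readings before a patient leaves usually carry most of that protection. With baseline and week 2 only, a missing week-2 home value is in effect predicted from the patient's baseline and from the patients in the same arm who stayed.

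If patients leave partly because of how their home SBP is responding, and this works differently in the two arms, those who stay no longer represent their arm. For example, if placebo patients with rising SBP leave while drug-arm dropout is random, the remaining placebo patients look better and the drug effect is understated. Other patterns overstate it. What is at stake is the home part of one secondary outcome.

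**Working it through.** **The plan's own figure.** n per group = 2 × (1.960 + 0.842)² × 7.5² / 5.0² = 35.3, rounded up to 36; 72 in total; 72 / 0.90 = 80. This reproduces. It concerns nighttime SBP and is not changed by this point.

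**Inputs.** From the documents: 10% withdrawal, not split by arm; and, borrowed from the nighttime calculation, an effect of -5.0 mmHg with SD of change 7.5 mmHg. The documents give no effect, SD, correlation or dropout pattern for home SBP, so those below are assumptions.

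**Check A: one-sided dropout, by formula.** Assume a true effect of -3 mmHg, SD of change 8 mmHg, and a week-1/week-2 correlation r of 0.6 to 0.8. Drug-arm dropout is random. Placebo dropouts are the 10% with the highest week-1 change plus independent noise of SD 8.

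- Shift in mean week-1 change among placebo stayers = -8 × (1/√2) × φ(1.282)/0.90 = -8 × 0.707 × 0.195 = -1.10 mmHg.
- Shift at week 2 = r × (-1.10) = -0.66 (r = 0.6) or -0.88 (r = 0.8).
- Week-2-only estimate = -3 + 0.66 = -2.34, or -3 + 0.88 = -2.12 mmHg. Simulation with 40 per arm gives -2.4 to -2.1.
- With the week-1 mean in the model, the simulated estimate is -3.0.
- Standard error with 36 completers per arm = 8 × √(2/36) = 1.89 mmHg, so the bias is 0.66/1.89 = 0.35 to 0.88/1.89 = 0.47 of a standard error.
- With the same mechanism and the same rate in both arms, the shifts cancel and the estimate is -3.0.

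**Check B: likelihood estimate with baseline in the model.** Large-sample simulation (400,000 per arm) with true effect -5, SD of change 7.5, within-visit SD 12 (baseline/week-2 correlation 1 - 56.25/(2 × 144) = 0.805), and week-1/week-2 correlation 0.85 to 0.92. Dropout on suvorexant/placebo was 10/10%, 15/5% or 20/0%, averaging 10%. A positive bias means that the benefit is understated.

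| Dropout depends on | Bias, two time points (mmHg) |
|---|---|
| Arm only, up to 20% vs 0% | within 0.03 |
| Baseline only | within 0.05 |
| Week-1 change, same direction, equal rates | within 0.03 |
| Week-1 change, moderate, same direction, unequal rates | -0.30 to -0.86 |
| Week-1 change, moderate, opposite directions | 0.58 to 0.89 |
| Week-1 change, deterministic, differing by arm | 0.72 to 2.10 in size |

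Adding week 1 brings the bias within 0.05 in every row. The largest moderate case (0.89, at 20/0%) has a standard error of about 7.5 × √(1/32 + 1/40) = 1.78, so the ratio is 0.50.

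**Check C: dropout driven by the week-2 value itself.** In the setting of Check A, but with placebo dropout depending on week 2, the stayers' shift is the full -1.10 and the week-2-only estimate is -3 + 1.10 = -1.9. With week 1 added, the simulated estimate is -2.3 to -2.6. The bias is reduced but not removed.

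**Check D: precision under random dropout.** Ratio of standard errors, with week 1 to without = √(1 - 0.10 × r²), which is √(1 - 0.036) = 0.982 at r = 0.6 and √(1 - 0.064) = 0.967 at r = 0.8. The gain is about 2 to 3%.

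**The case against.** The strongest reply is that the model matches the stated outcome, a week-0 to week-2 change; that withdrawal over two weeks is planned at only 10%; and that nothing in the documents suggests SBP-driven dropout differing by arm. The one-sided pattern in Check A is a chosen scenario. A milder one, a single SBP-related dropout threshold applied to both arms at 10% overall (about 12% on placebo and 8% on drug), moves a true -3 to about -2.7, a bias of 0.25 to 0.33 mmHg. Complete removal of the bias in Checks A and B is also partly built in, because dropout was generated from the readings that were then added to the model. All of this stands, and it makes the point small. It does not give a reason to leave collected data out.

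Three stronger readings are tempting, and the documents do not support them.

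- *Any imbalance in dropout between arms biases the result.* It does not. Group and group-by-time are in the model, and dropout differing only by arm gave about zero bias even at 20% against 0%.
- *Every on-treatment home reading of every early stopper is lost.* This is not shown. The week-2 window is undefined, so a patient stopping late in week 2 may still have a value. Note 5 does not tie home readings to continued treatment.
- *The primary result is at risk.* It is sleep SBP by ABPM, for which two time points fit the schedule.

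One could also read the MMRM as meant for ABPM only, with home change compared by the t-test named for continuous variables. That would use no more of the intermediate readings.

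**Conclusion.** The point holds as a low-cost improvement to the home part of one secondary outcome. A patient without a week-2 home value contributes baseline only, although earlier on-treatment readings may exist. Bias arises only if dropout depends on on-treatment home SBP, beyond arm and baseline, and differently in the two arms. In that case it is roughly 0.3 to 0.9 mmHg in either direction at an average 10% withdrawal, or at most about half a standard error. Deterministic dropout, an extreme case, reaches about 2.1 mmHg. These sizes rest on assumed home SBP effects, SDs, correlations and dropout patterns; only the 10% comes from the plan as a withdrawal figure. The sample size and the ABPM analyses are unaffected.

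**What to change.** For morning home SBP, fit the MMRM with three time points (baseline, week-1 mean, week-2 mean) and an unstructured covariance, and report the week-2 group contrast as the result. Fix in advance which days make up each of the three means. Patients who stop early then contribute the weeks that they recorded. Leave the ABPM model at two time points.

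The cost is a sentence or two in the Statistical Analysis section, settled before unblinding. The readings are already scheduled, no patients or visits are added, and the covariance needs 3 × 4 / 2 = 6 parameters, which 72 to 80 patients can support. The change removes the bias when dropout depends on week-1 readings, reduces it when dropout depends on later values, and lowers the standard error by about 2 to 3% if 10% drop out at random.
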